6.2.3. Fraction of PF-07321332 (nirmatrelvir) dose removed from the body by dialysis (F_d)

Fraction of nirmatrelvir dose removed from the body by dialysis (F_d) will be calculated as follow:

[figure not shown]
$$F_d = 100\% \times A_d / Dose$$

where A_d is the amount of drug removed by the dialysis and is calculated as follows:

[figure not shown]
$$A_d = CL_d \times AUC_{t_0-t_1}$$

where for $AUC_{t_0-t_1}$, t_0 marks the start time and t_1 the termination of the hemodialysis session.

CCI

CCI

CCI

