Participant-completed electronic diary (study intervention log)		Day 1 through Day 5							
 
The electronic diary will be provided or application downloaded to participant's own device and training completed at the Baseline visit.
 
Daily dosing will be entered in an electronic diary Days 1 through Day 5. The Day 1 dose at the site should be entered in the eDiary by the participant (or caregiver) while on site.
 
For participants who are using an eDiary provided through the study, the eDiary will be collected on Day 5, the next scheduled visit or ET visit after completion of dosing log entries on the device.
 

PFIZER CONFIDENTIAL

Visit Identifier	Screening	Baseline (Day 1)	Day 5	Day 10	Day 14	Day 21	Day 34	ET	Notes
Visit Window	Day -1 to Day 1	0 days	0 days	±1 day	±2 days	±2 days	±3 days		
Type of Visit	In-Person Site or Home Health Visit with Telehealth	In-Person Site Visit	In-Person Site or Home Health Visit	Telehealth Visit	In-Person Site, Home Health or Telehealth Visit	Telehealth Visit	In-Person Site, Home Health or Telehealth Visit	In-Person Site, Home Health or Telehealth Visit	
Investigational Site check of participant eDiary dosing entries		Day 1 through Day 5							
 
On Days 1-5, site personnel will review eDiary participant dosing entries daily on the Trial Manager portal and contact participant if not completed.
 
See Section 6.5.
 

Record HD Details (Cohort 2 only)		HD Days during Day 1 through Day 5							
 
During HD treatment, site staff should record relevant HD details on the designated CRF.
 

Retrieval of unused study intervention and empty study intervention containers			X		[X]			[X]	
 
If the Day 5 visit is conducted prior to last dose of study intervention on Day 5, empty study intervention containers, and unused study intervention should be returned at the next in-person visit (Day 14). The electronic diary should be reviewed and device should be returned if applicable.
 
See Section 6.5.
 

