**PK SAMPLING SCHEMA 2 – COHORT 2: HD cohort with 1st Dose on HD day that is Monday**

Study Day	Day 1 – HD MONDAY	Day 2 – no HD TUESDAY	Day 3 – HD WEDNESDAY	Day 4 – no HD THURSDAY				Day 5 – HD FRIDAY
PF-07321332 (nirmatrelvir)/ritonavir administration	X b	X	X b		X			X b
Hours after dosea	1 – 3		Before and During HD	0	0.5 – 3	4 – 8	9 – 15	Before HD start
PK blood sampling (Tasso)	X f		X c	X c	X f	X f	X f	[X c ]
PK blood sampling during HD (arterial and venous ports)			X d					X e
Hematology blood sample (hematocrit)			X i					
Blood:Plasma Ratio sample (venous)	X h		X g, h		X h			[X g, h ]

- a. Hours are in reference to the QD dose of PF-07321332 (nirmatrelvir)/ritonavir on each study day. The Day 1 dose should be taken at the clinic visit.
- b. On dialysis days, participants will take study intervention as soon as feasible after HD.
- c. Tasso blood sample: Tasso device placed by participant, caregiver, home health provider, or other healthcare provider (as appropriate).
- d. Venous blood samples: HD staff to obtain PK blood samples from the HD filter arterial port and the venous port at 0 hr (prior to start of HD) and at 0.5, 1, 2, 3, and 4 hours post start of dialysis.
- e. Day 5 PK blood sample: If participant goes to HD treatment prior to going to investigational site on Day 5, then HD staff to obtain this venous sample prior to the start of dialysis from the venous HD line. If participant goes to investigational site prior to going to HD on Day 5, then investigational site staff can obtain PK sample using the Tasso device.
- f. Tasso blood samples: After dosing study drug, Tasso device placed by participant, caregiver, home health provider, or other healthcare provider (as appropriate). Collect the consecutive PK samples within the prescribed windows with each sample taken a minimum of 2 hours apart.
- g. Blood:Plasma Ratio venous sample: Collect at 0 hr prior to start of HD.

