For PK assessments in severe renal impairment participants on HD, samples will be collected on Days 1 through 5 of dosing with respect to the participant's dialysis sessions during treatment. If at home, this should be collected using a Tasso device or may be done at an in-person visit, unless otherwise specified in the [SoA](#). During HD, venous port (entering dialyzer) and arterial port (exiting the dialyzer) blood samples will be collected at 0, 0.5, 1, 2, 3 and 4 hours post the start of dialysis.

This study will use the program-level E-DMC. The E-DMC is independent of the study team and includes only external members. The E-DMC charter describes the role of the E-DMC in more detail for this study.

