### Additional Inclusion Criteria for Cohort 2 (Receiving HD):

6. Receiving stable intermittent HD for at least 6 weeks prior to Screening.

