### 8.5.2. Hemodialysis

Participants assigned to Cohort 2 will begin study intervention either on a HD treatment day or non-HD treatment day. The day of the participant's first IP dose, either on an HD day or on a non-HD day (ie, Treatment Day 1) will determine the subsequent PK sample schedule as described in the [PK Sampling Schema](#).

Participants beginning IP administration on an HD treatment day (ie, Treatment Day 1) will have PK samples collected per the [PK Sampling schema](#) in Section 1.3 including samples drawn from HD lines before and during HD treatment days. Obtain blood samples for **hematology (hematocrit)** at time 0 (venous port sample) and time of the last PK draw (venous port sample) on dialysis, to be used for dialysis clearance (CLd) calculations. Time 0 is defined as the time period prior to the start of the HD blood pump.

If the participant is assigned to begin IP treatment (ie, Treatment Day 1) on a non-HD day, the participant will have samples collected per the [PK Sampling Schema](#) in Section 1.3. Obtain blood samples for hematology (hematocrit) at time 0 (venous port sample) and time of the last PK draw (venous port sample) on dialysis, to be used for dialysis clearance (CLd) calculations. Time 0 is defined as the time period prior to the start of the HD blood pump.

Additional details regarding the HD treatment will be captured in the database (refer to CRF completion guidelines).

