### **8.5.3. PK Samples for Analysis of PF-07321332 (nirmatrelvir) and Ritonavir**

PK samples for measurement of PF-07321332 (nirmatrelvir) and ritonavir plasma concentrations will be collected, using Tasso M20 device for dried blood. If Tasso device is not available or unable to function properly, then a venous blood sample must be drawn. For plasma samples, a blood sample of approximately 4 mL, to provide approximately 1.5 mL plasma, will be collected for measurement of plasma concentrations of PF-07321332 (nirmatrelvir) and ritonavir as specified in the [SoA](#). For Tasso sampling, approximately 100  $\mu$ L of blood is collected. Instructions for the collection, handling, and recording of biological samples will be provided in the laboratory manual or by the sponsor. The date and time (12-hour clock time) of collection for each sample will be recorded on the sample requisition forms that are submitted to the laboratories.

The ritonavir concentration will be measured using Tasso samples collected and/or venous blood sample collected and will be reported as plasma concentration listings only (no PK analysis of ritonavir data).

If a participant cannot attend a clinic visit, PK samples may be collected via home health visit, self-collected or caregiver-collected using the Tasso M20 device to collect whole blood microsamples to measure PF-07321332 (nirmatrelvir) and ritonavir concentrations.

The actual times may change, but the number of samples will remain the same. All efforts will be made to obtain the samples per the PK sampling times in Section [1.3](#) relative to dosing.

Both Tasso sample and venous blood samples will be used to evaluate the PK of PF-07321332 (nirmatrelvir) and ritonavir. Samples collected for analyses of PF-07321332 (nirmatrelvir) and ritonavir concentrations may also be used to evaluate safety or efficacy aspects related to concerns arising during or after the study, for metabolite identification and/or evaluation of the bioanalytical method [CCI](#) [REDACTED].

Genetic analyses will not be performed on these plasma samples unless consent for this was included in the informed consent. Participant confidentiality will be maintained.

Samples collected for measurement of plasma concentrations of PF-07321332 (nirmatrelvir) and ritonavir will be analyzed using a validated analytical method in compliance with applicable SOPs. Potential metabolites may be analyzed with [CCI](#) [REDACTED] validated [CCI](#) [REDACTED] methods.

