6.2.2. HD clearance (CL_d) of PF-07321332 (nirmatrelvir)

Hemodialysis clearance (CL_d) of nirmatrelvir will be calculated using the following relationship:

$$CL_d = [(C_{in} - C_{out}) / C_{in}] \times [Q_b \times (1 - HCT)]$$

where C_{in} and C_{out} are plasma concentrations measured in blood samples entering and exiting the dialyzer, respectively; Q_b and HCT are blood flow rate entering the dialyzer and hematocrit measured at each collection time, respectively. Individual time point CL_d values obtained using this method will be used to calculate an average subject CL_d.

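### The AUC behind the fraction of dose removed (Fd) runs to the end of dialysis, but the last dialyzer pair is scheduled at 4 h and session length is not fixed

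*SAP*

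**What the plan says.** SAP 6.2.3 defines Fd as 100% × Ad/Dose, with Ad = CLd × AUC(t0–t1), where "t_0 marks the start time and t_1 the termination of the hemodialysis session". SAP 6.2.2 calculates CLd at each collection time from the inlet and outlet concentrations, blood flow and hematocrit, and then: "Individual time point CL_d values obtained using this method will be used to calculate an average subject CL_d".

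The sampling runs on a clock. Schema 2, footnote d, has port samples taken "at 0 hr (prior to start of HD) and at 0.5, 1, 2, 3, and 4 hours post start of dialysis". Schemas 3 to 7 use the same times, and Schemas 8 to 12 do too, apart from listing 0 h twice. Protocol 4.1 agrees: "blood samples will be collected at 0, 0.5, 1, 2, 3 and 4 hours post the start of dialysis".

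Nothing fixes the length of a session. The entry criterion for Cohort 2 is "Receiving stable intermittent HD for at least 6 weeks prior to Screening". Protocol 4.2 gives a frequency of three sessions a week but no duration. Two provisions bear on timing in general. The Schedule of Activities says "During HD treatment, site staff should record relevant HD details on the designated CRF", without listing the fields, and Protocol 8.5.3 says "The actual times may change, but the number of samples will remain the same". Neither ties the last draw to the end of the session.

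**The concern.** The integral ends at an event and the sampling ends at a clock time. The two are certain to coincide only when the session lasts 4 h. If it runs longer, the AUC after 4 h has no sample. If it stops between 3 h and 4 h, the last pair drawn during dialysis is at 3 h, and a pair drawn at 4 h would describe blood that is no longer being dialyzed.

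Later samples cannot fill the gap. The dose follows dialysis as soon as feasible, so in Schemas 2 to 10 the next PK sample already reflects a new dose. In Schemas 11 and 12 the port-sampled session is on Day 5 and no PK sample follows it.

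CLd and Fd are the only endpoints listed for the objective on the effect of hemodialysis. They come from about 12 participants with one port-sampled session each, so session-level error is not averaged out within a participant. Any relative error in the AUC passes unchanged to Ad and Fd.

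**Working it through.** The documents give no figure for session length, intradialytic AUC, Ad or Fd, so there is no plan figure to reproduce. What follows is an illustration under stated assumptions.

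**Inputs from the documents.** Sampling times 0, 0.5, 1, 2, 3 and 4 h (Protocol 4.1 and Schemas 2 to 12); limits of integration t0 to t1 (SAP 6.2.3); simple averaging of time-point CLd values (SAP 6.2.2); off-dialysis half-life 13.37 h after a single dose in severe renal impairment (Protocol Table 1).

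**Assumptions.** Inlet concentration falls mono-exponentially during dialysis by a fraction d = 0.3, 0.5 or 0.7 over 4 h, so k = −ln(1 − d)/4. Session lengths of 3.5, 5 and 6 h are hypothetical.

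**Share of session AUC beyond the last on-dialysis sample.** With the last sample at time s and the session ending at T, share = 1 − (1 − e^(−ks))/(1 − e^(−kT)).

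- T = 3.5 h, s = 3 h. For d = 0.3: 1 − 0.23472/0.26809 = 12.4%. For d = 0.7: 1 − 0.59464/0.65127 = 8.7%.
- T = 5 h, s = 4 h. For d = 0.3: 1 − 0.3/0.3597 = 16.6%. For d = 0.7: 1 − 0.7/0.7780 = 10.0%.
- T = 6 h, s = 4 h. For d = 0.3: 1 − 0.3/0.4143 = 27.6%. For d = 0.7: 1 − 0.7/0.8357 = 16.2%.

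| Session | d = 0.3 | d = 0.5 | d = 0.7 |
|---|---|---|---|
| 3.5 h | 12.4% | 10.9% | 8.7% |
| 4 h | 0% | 0% | 0% |
| 5 h | 16.6% | 13.7% | 10.0% |
| 6 h | 27.6% | 22.7% | 16.2% |

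A slower decline makes the share larger. If the on-dialysis half-life were as long as the 13.37 h off dialysis, the shares would be 13.2%, 18.0% and 29.9% for 3.5, 5 and 6 h.

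**Effect of one off-dialysis pair on CLd.** Suppose the pair at 4 h has zero extraction and the others are equal. With five post-start pairs, the mean is 4/5 = 0.80 of the on-dialysis value, a fall of 20%. With six pairs, counting 0 h as one of the equal ones, it is 5/6 = 0.833, a fall of 16.7%. Fd falls by the same proportion, separately from any AUC error. The 0 h pair needs a rule as well, since Protocol 8.5.2 says "Time 0 is defined as the time period prior to the start of the HD blood pump".

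**Check on moving the last pair.** In a 6 h session sampled at 0, 0.5, 1, 2, 3 and 6 h, the linear trapezoidal AUC exceeds the exact value by 0.3% (d = 0.3) to 2.3% (d = 0.7). That compares with 16 to 28% beyond the last sample under the current times.

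**The case against.** The strongest reply is that the SAP already names the right limit, so an analyst who follows it will extrapolate. Under the mono-exponential model used above, log-linear extrapolation from the on-dialysis samples recovers the tail exactly. This stands: the percentages describe AUC that is unobserved, and a reader who takes them as bias in Fd goes further than the text allows.

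The protocol also describes the port samples as taken during dialysis and ties the second hematocrit to the last draw on dialysis, and Protocol 8.5.3 lets times move. A careful site could therefore bring the last pair forward in a short session. That is fair, but no instruction tells it to, and SAP 6.2.2 would not exclude a late pair if one were drawn.

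Three further inferences are not supported:

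- That CLd is also wrong in long sessions. It uses no AUC, so a session over 4 h leaves its calculation intact.
- That the AUC will overrun in short sessions. Integrating to a post-dialysis 4 h sample would contradict the SAP's own limit.
- That no other sample is taken at the end of dialysis. Schemas 8 to 12 have bracketed Tasso and venous blood-to-plasma samples at the end of the Day 2 session, and Schema 11 footnote f mentions a venous-port sample at the end of dialysis, although no table cell refers to it. The column samples belong to Day 2, whereas the CLd session is on Day 4 or 5. Footnote f is a single sample whose wording matches the Day 2 column. None supplies an end-of-session pair for the CLd session.

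Finally, SAP Appendix 2.2 refers endpoint derivations to an Analysis and Reporting Plan that was not available, and parts of the SAP are redacted. A rule may exist there.

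**Conclusion.** The mismatch between the sampled interval and the integrated interval is in the text, and the protocol and SAP as supplied contain no rule to bridge it. It mainly affects Fd. CLd is exposed only in sessions shorter than 4 h, and only if an off-dialysis pair enters the average; the fall is then about 17 to 20% if that pair shows zero extraction.

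The unobserved share of AUC is about 9 to 12% for 3.5 h, 10 to 17% for 5 h and 16 to 28% for 6 h. This rests on an assumed mono-exponential fall of 30 to 70% over 4 h and on hypothetical session lengths. Without extrapolation in sessions over 4 h, or if the AUC is cut at 3 h in a 3.5 h session, Ad and Fd are too low by that share.

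A reader might infer that every session not lasting 4 h gives a wrong Fd. The documents do not support that: extrapolation can cover the tail, and a session ending at 3 h already has a pair at its end, provided any 4 h pair is left out. This is a worthwhile, inexpensive improvement to a descriptive secondary endpoint and does not show that the endpoint will be biased.

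**What to change.** **Protocol 4.1 and the port-sampling footnotes of Schemas 2 to 12.** Replace the scheduled 4 h pair with an end-of-dialysis pair drawn shortly before the blood pump stops. Record the actual draw time and the actual start and stop times of the session. The second hematocrit, already tied to the last draw, moves with it.

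**SAP 6.2.2.** Admit only pairs drawn during dialysis to the CLd average, and say explicitly whether the 0 h pair counts.

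**SAP 6.2.3.** Define t1 as the recorded stop time. Calculate AUC(t0–t1) from on-dialysis inlet samples at actual times, with log-linear extrapolation over any short remainder between the last sample and t1.

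If the sampling can no longer be changed, the two SAP edits are still worth making on their own.

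**Cost.** Footnote wording and instructions to the dialysis units; the tube count is unchanged. The last sampling time will vary between participants, and long sessions will have a wider gap before the last sample (3 h in a 6 h session, costing at most about 2.3% in trapezoidal error under the assumptions above). A session that stops unexpectedly may still lack its final pair, and the extrapolation rule then applies.

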6.4. Subset Analyses

Not applicable.

6.5. Baseline and Other Summaries and Analyses

6.5.1. Baseline Summaries

Baseline demographic and other characteristics described in 3.4 will be tabulated for the SAS and summarized by cohort, and overall. Quantitative variables will be described by standard descriptive statistics (N, mean, standard deviation, median, minimum, and maximum), and qualitative variables will be summarized by number and proportion in each category.

Demographic data collected at screening will be reported.

6.5.2. Study Conduct and Participant Disposition

The number of participants screened, assigned to study treatment, completing study treatment, and completing the study will be summarized. The reasons for discontinuation will be summarized by cohort.

6.5.3. Study Treatment Exposure

The number of doses of the study treatment received and the percentage compliance will be summarized.

6.5.4. Concomitant Medications and Nondrug Treatments

Concomitant medications and non-drug treatments will be summarized by cohort in accordance with CDISC and CaPS standards.

The types of vaccines received will be summarized for number and percent of participants for each vaccine type overall and each cohort.

6.5.5. Vaccination

Vaccination data will be collected in con-med data set (ADCM), the variable MCAT represents the type of vaccine (i.e., Pfizer, J&J and others). For participant who have more than one dose of vaccine, there are more than one record in the ADCM data set. So the number of doses can be derived from the record.

The number of doses received will be summarized for number and percent of subject for each vaccine dose overall and each cohort.

6.6. Safety Summaries and Analyses

All safety analyses will be performed on the safety population, ie, Safety Analysis Set (SAS). Safety summaries and analyses will utilize CDISC and CaPS standards.

6.6.1. Adverse Events

As this study has only one treatment, the 3-tier approach to adverse event reporting will not be utilized. For each AE, the number and percent incidence will be summarized by cohort, but the incidence will not be formally compared among cohorts. No p-values or confidence intervals will be generated and therefore, no multiplicity adjustment will be used. AEs will be arranged alphabetically within system organ class in the summary tables.

It should be recognized that most studies are not designed to reliably demonstrate a causal relationship between the use of a pharmaceutical product and an adverse event or a group of adverse events. Except for select events in unique situations, studies do not employ formal adjudication procedures for the purpose of event classification. As such, safety analysis is generally considered as an exploratory analysis and its purpose is to generate hypotheses for further investigation.

6.6.2. Laboratory Data

Lab data and the corresponding changes from baseline will be summarized over time (Day 1, 5) by cohort, and overall using standard descriptive statistics. Any abnormalities of potential clinical concern according to the criteria specified by the Pfizer reporting standards will be described. Data will be presented in tabular and/or graphical format, as appropriate.

Data collected at screening that are used for inclusion/exclusion criteria will be considered source data, and will not be required to be reported, unless otherwise noted.

6.6.3. Vital Signs

SBP, DBP, pulse rate, respiratory rate, oral temperature, and SpO₂ will be summarized over time (Day 1, 5, 14, 34) by cohort, and overall using standard descriptive statistics. Any abnormalities of potential clinical concern (see Table 5) will be described. Data will be presented in tabular and/or graphical format, as appropriate.

Table 5. Post-Baseline Vital Signs Categories

Parameter (units)	Criteria
Systolic Blood Pressure (mmHg)	Value < 90
	Increase \geq 30
	Decrease \geq 30
Diastolic Blood Pressure (mmHg)	Value < 50
	Increase \geq 20
	Decrease \geq 20
Pulse Rate (bpm)	Value < 40
	Value > 120

6.6.4. Electrocardiograms

Not applicable.

6.6.5. Physical Examination

Medical history and physical examination collected during the course of the study will be considered source data and will not be required to be reported, unless otherwise noted. However, any untoward findings identified on physical and/or neurological examinations conducted during the active collection period will be captured as AEs, if those findings meet the definition of an AE.

7. INTERIM ANALYSES

No interim analysis will be conducted for this study.

As this is an open-label, unblinded study, the sponsor may conduct reviews of the data during the study for the purpose of safety assessment, facilitating PK/PD modeling, and/or supporting clinical development.

8. REFERENCES

None.

9. APPENDICES

Appendix 1. Summary of PK Concentration Analyses

Endpoint	Analysis Type	Population	Data Inclusion and Rules for Handling Intercurrent Events and Missing Data	Analysis Model
PK concentration	Summary (nominal sampling time)	PK concentration analysis set	Missing data will not be imputed. Concentrations BLQ imputed as zero.	Descriptive stats for overall, Cohort 1 and Cohort 2
	Figure – Individual concentration vs. time profiles (actual sampling time)	PK concentration analysis set	Missing data will not be imputed. Concentrations BLQ imputed as zero.	Spaghetti plots for Cohort 1, Cohort 2
	Figure – Median concentration vs. time profile (nominal sampling time)	PK concentration analysis set	Missing data will not be imputed. Concentrations BLQ imputed as zero.	Summary plots for Cohort 1 and Cohort 2
	Listing (nominal sampling time)	PK concentration analysis set	Concentrations BLQ reported as such.	Listing by cohort, participant, nominal sampling time; includes method of blood collection, actual sampling time, and deviation from nominal sampling time

